### 3.2.3. Other Secondary Endpoints:

Efficacy as measured by:

- The percentage of subjects with no Mycologically Proven Recurrence up to Week 4, Week 8, Week 12, and Week 36 (end of follow-up [EOFU]);
- The time to the first Recurrence (Mycologically Proven, Presumed or Suspected) of VVC through EOFU;
- The percentage of subjects with Mycological Eradication (negative fungal culture) at Week 12, Week 24 (TOC) and Week 36 (EOFU);
- The percentage of subjects with no Mycologically Proven, Presumed or Suspected Recurrences up to Week 4, Week 8, Week 12 and Week 36 (EOFU);
- The percentage of subjects with no Mycologically Proven or Presumed Recurrences up to Week 4, Week 8, Week 12, Week 24 (TOC) and Week 36 (EOFU);
- The proportion of subjects in four ordered categories related to the number of Recurrences (Mycologically Proven, Presumed or Suspected) of VVC from Baseline (Day 1) to Week 24 (TOC) and Week 36 (EOFU). The three categories of recurrence are defined as (i) 0 episode, (ii) 1 episode, (iii) 2 to 3 episodes, and (iv)  $\geq 4$  episodes;
- The absolute number of Mycologically Proven, Presumed or Suspected Recurrences from Baseline (Day 1) to Week 24 (TOC) and Week 36 (EOFU);
- Absolute improvement in QOL outcomes at Week 12, Week 24 (TOC) and Week 36 (EOFU) as measured by EQ-5D, SF-36 and FSDDS;

Safety and tolerability as measured by:

- Adverse events (AEs), vital signs, treatment discontinuation and safety laboratory tests.

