##### 4.1. Sample Size

The primary endpoint of the study is the percentage of subjects with documented Clinical Success up to Week 24 (TOC). Assuming response rates of 65% and 43% for ibrexafungerp and placebo, respectively; 90% power; and an alpha level of 0.05, approximately 240 subjects randomized at a

1:1 ratio are needed to declare a difference between ibrexafungerp and placebo at Week 24 based on Fisher's Exact test.

In order to be randomized, a subject should have achieved the proposed significant resolution of signs and symptoms (total composite score  $\leq 2$  on the VSS Scale) after receiving fluconazole therapy for an acute episode and have a positive culture for *Candida* spp. from the sample collected at screening. It is estimated that approximately 320 subjects will need to enter the Acute Phase to provide 240 subjects randomized to the Prevention of Recurrence Phase. Enrollment into the Acute Phase will be discontinued when approximately 240 subjects have been randomized.

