The summary of the absolute number of recurrences from Baseline (Day 1) to Week 24 (TOC) and Week 36 (EOFU) will be presented by recurrence categories and overall, a two-way analysis of variance (ANOVA) model including effects for treatment group and Country will be performed. For individual treatment group and ibrexafungerp 300-mg BID comparison versus placebo, the least squares mean, associate standard error (SE), 95% confidence interval and corresponding p-value will be presented. Additionally, same analysis will be performed to only include those subjects who completed the specified visit based on the ITT set.

For the below ordered categorical endpoint, a proportional odds model will be fitted accounting for the effects of treatment, Country, and uncontrolled diabetes mellitus (Yes or No) at baseline. The proportional odds model will fit an ordered regression model for the ordinal dependent variable as described by McCullagh (1980). If the assumption of proportional odds is violated, alternative analyses will be considered which require a weaker assumption. The p-value, relative risk and 95% CI will be presented in the ibrexafungerp 300-mg treatment group compared to the placebo arm.

- The proportion of subjects in four ordered categories related to the number of Recurrences (Mycologically Proven, Presumed or Suspected) of VVC from Baseline (Day 1) to Week 24 (TOC) and Week 36 (EOFU). The four categories of recurrence are defined as (i) 0 episode, (ii) 1 episode, (iii) 2 to 3 episodes, and (iv)  $\geq 4$  episodes

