#### **11. Changes in the Planned Analysis**

The following have changed from the protocol:

- For the continuous efficacy endpoints except for the absolute number of Mycologically Proven, Presumed or Suspected Recurrences from Baseline (Day 1) to Week 24 (TOC) and Week 36 (EOFU), a Mixed-Effect Model for Repeated Measure (MMRM) analysis model and an analysis of covariance (ANCOVA) model are recommended rather than a two-way ANOVA model. Baseline value will be considered as possible contributor to any observed differences. Additionally, other variables may be considered during blinded data review.
- Add the randomization stratification factor, uncontrolled diabetes mellitus (Yes or No), as justification factor in the efficacy analyses models.

- For efficacy analyses, Country is recommended rather than site to be used as the justification factor.
- In protocol, it stated that the safety and tolerability as measured by AEs, vital signs, treatment discontinuation and safety laboratory tests at TOC (Week 24). The texts “at TOC (Week 24)” is removed since all safety data captured in this study will be taken into account for analysis.
- Intent-to-treat (ITT) Set definition was changed to be “All randomized subjects who signed the consent form and received at least one dose of study drug (ibrexafungerp or placebo).”
- Modified Intent-to-treat (mITT) Set definition was changed to be “All randomized subjects who signed the consent form and received at least one dose of study drug (ibrexafungerp or placebo), who have a confirmed mycological culture for yeast at Screening and a negative culture for yeast at Baseline (Day 1).”
- The number of recurrence episodes will be classified to 4 order categories for analysis rather than 3 categories as mentioned in the protocol. Updated based on client’s request.

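### The recurrence count is analysed by a pooled-variance ANOVA with no follow-up time, so each arm's 95% CI misses its level and no rule covers the counts of early leavers

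*SAP*

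**What the plan says.** The endpoint in SAP 3.2.3 is "The absolute number of Mycologically Proven, Presumed or Suspected Recurrences from Baseline (Day 1) to Week 24 (TOC) and Week 36 (EOFU"): a number over a fixed period, not a rate. SAP 8.2.1 analyses it by "a two-way analysis of variance (ANOVA) model including effects for treatment group and Country will be performed". The output covers each arm as well as the contrast: "For individual treatment group and ibrexafungerp 300-mg BID comparison versus placebo, the least squares mean, associate standard error (SE), 95% confidence interval" and a p-value. A repeat is planned in which the "same analysis will be performed to only include those subjects who completed the specified visit based on the ITT set".

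The ANOVA was kept deliberately. SAP Section 11 moves other outcomes to MMRM and ANCOVA with the words "For the continuous efficacy endpoints except for the absolute number of Mycologically Proven, Presumed or Suspected Recurrences".

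No missing-data rule yields a count. SAP 4.4.1 (non-responder imputation) is headed as applying to categorical responses. Its text cites 8.2.1, but it assigns failure, not a number of episodes. SAP 4.4.2 (LOCF) covers quality-of-life scores. Protocol 18.4 assigns treatment failure when the Week 24 assessment is absent, and Protocol 18.0 otherwise analyses data without imputation.

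**The concern.** A small count with different means in the two arms has different variances too. An ANOVA with one pooled variance gives both arms the same standard error, apart from small design effects. That is too small for the arm with more recurrences and too large for the arm with fewer.

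The second issue is time at risk. Consider a woman who leaves at Week 6 without a recurrence. She is a failure in the primary analysis and is censored in the time-to-first-recurrence analysis. If the count is taken as observed, she contributes zero recurrences to Week 24 and again to Week 36. Within SAP 8.2.1, follow-up time is therefore respected for the first recurrence and ignored for the number of recurrences.

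The number of recurrences is a named secondary objective (SAP 2.3), and this is the only planned estimate of episodes per woman. The ordinal model compares categories, and Kaplan-Meier stops at the first episode.

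**Working it through.** **Inputs.** SAP 4.1: "Assuming response rates of 65% and 43% for ibrexafungerp and placebo, respectively; 90% power; and an alpha level of 0.05", with "approximately 240 subjects randomized at a" "1:1 ratio are needed to declare a difference between ibrexafungerp and placebo at Week 24", so 120 per arm. The plan's own figure reproduces: exact two-sided Fisher power at 120 per arm is 90.9%. The documents give no mean count, dispersion or dropout rate, so these are assumed and shown as ranges.

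**Step 1: mean counts.** Take 65% and 43% as the probabilities of no recurrence by Week 24. For a Poisson count the mean is -ln(P0): -ln(0.65) = 0.431 and -ln(0.43) = 0.844. For a negative binomial with dispersion k, P0 = (1 + k·mean)^(-1/k) and the variance is mean + k·mean².

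**Step 2: arm-level coverage, full follow-up.** With equal arms the pooled variance is the average of the two arm variances, and

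coverage = 2Φ(1.96 × √(pooled variance / arm variance)) - 1.

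Poisson: pooled variance = (0.431 + 0.844)/2 = 0.6375. For placebo, √(0.6375/0.844) = 0.869 and 1.96 × 0.869 = 1.703, giving 91.1%. For ibrexafungerp, √(0.6375/0.431) = 1.216 and 1.96 × 1.216 = 2.384, giving 98.3%.

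| Distribution | Means (ibrexafungerp, placebo) | Variances | Coverage, ibrexafungerp | Coverage, placebo |
|---|---|---|---|---|
| Poisson | 0.431, 0.844 | 0.431, 0.844 | 98.3% | 91.1% |
| k = 0.5 | 0.481, 1.050 | 0.596, 1.601 | 99.2% | 89.6% |
| k = 1 | 0.538, 1.326 | 0.828, 3.083 | 99.7% | 88.2% |

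Simulation at 120 per arm agrees: about 88-91% on placebo and 98-99.6% on ibrexafungerp. With four countries in the ANOVA (assumed shares 55/15/15/15%), the Poisson case gave 97.9% and 91.5%. Capping Poisson counts at two episodes gives 97.3% and 92.5%. Only strictly 0/1 counts come close to nominal (95.4% and 94.6%), and SAP 8.2.1 itself provides for 2 to 3 and for 4 or more episodes.

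**Step 3: the between-arm interval.** With n per arm, the true variance of the difference is (v1 + v2)/n. The pooled formula gives 2 × (v1 + v2)/2 ÷ n, which is the same. Simulated coverage with full follow-up was 94.4-95.5%.

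**Step 4: early leaving.** Assume leavers enter with the episodes seen so far and leave uniformly over the period, independently of recurrence. If a fraction d leaves, the arm mean is multiplied by 1 - d/2. The true Poisson difference is 0.431 - 0.844 = -0.413.

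- 15% in each arm: factor 0.925 in both, so the difference shrinks by 7.5%.
- 10% ibrexafungerp, 25% placebo: 0.431 × 0.95 - 0.844 × 0.875 = 0.409 - 0.739 = -0.329, about 20% smaller. At k = 1: 0.511 - 1.160 = -0.649 against -0.788, about 18% smaller. Simulated type I error under equal true rates was about 7-9%.
- 25% ibrexafungerp, 10% placebo: 0.377 - 0.802 = -0.425 against -0.413, so little change. The ratio of means moves from 0.51 to 0.47, in the drug's favour.

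**Step 5: the alternative.** A rate per arm with a log follow-up offset and robust SE gave simulated coverage of about 94-95% for each arm and for the rate ratio in every setting run. Under 10% v 20% dropout (Poisson) the rate ratio was 0.509 against a true 0.510.

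**The case against.** **The treatment comparison is sound in the simplest case.** This stands. A reader might infer that the ANOVA invalidates the test of ibrexafungerp against placebo. With 1:1 allocation and full follow-up it does not: the fault is in the arm-level intervals that the SAP promises to report.

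**Dropout does not always dilute the effect.** This also stands. With more leavers on ibrexafungerp, the absolute difference is about unchanged. The inflated type I error needs an assumed 15-point imbalance. Protocol 11.3 and 14.18.3 keep women in the study after a recurrence, and 11.3 asks for Week 24 or Week 36 procedures at discontinuation.

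**The SAP does not say that leavers count as having no further episodes.** Correct. That reading is inferred from the absence of any count imputation and from the separate completer repeat, which implies that the main analysis includes non-completers. The firm statement is that the rule is missing.

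**The completer repeat already deals with unequal follow-up.** Largely true when leaving is independent of recurrence: at 10% v 25% it returns a Poisson difference of about -0.413, with 93-96% coverage of the difference. A reader might conclude that it should be dropped because it selects on completing, but the simulation does not support that. An offset model also assumes independent leaving. The repeat does keep the pooled variance, and its placebo interval still covers only 87-91%.

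**The calibration counts missing data twice.** The 65% and 43% are Clinical Success rates that score missing as failure. If 10% or 20% of women were missing, P0 would be higher; Poisson coverage then becomes 98.8%/90.4% or 99.4%/89.1% (ibrexafungerp/placebo). The arm-level result gets slightly worse.

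**A log-link model fails for rare categories, and the adjusted model was not tested.** Both are fair. At an assumed mean of 0.02, an arm of 120 has no events with probability exp(-2.4) = 9%. The simulated alternative was an unadjusted rate with robust variance, not a regression with covariates.

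**Conclusion.** The arm-level 95% CIs for the number of recurrences do not have their stated level: about 88-91% on placebo and 98-99.6% on ibrexafungerp. This rests on an assumed count distribution (Poisson to dispersion 1) calibrated to the planning rates, with 120 per arm and full follow-up. The direction holds for every distribution tried; only 0/1 counts come close to nominal.

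The handling of early leavers is unspecified. If they enter as observed, the effect on the difference ranges from little change to a shrinkage of about 20% over the dropout patterns tried. The documents cannot say which applies, because they give no dropout rate.

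The documents do not support a stronger claim that the between-arm test is generally invalid or always biased against the drug. This is one of the other secondary endpoints, so the primary conclusion is untouched. The change is worth making but is not essential to the trial's main result.

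**What to change.** In SAP 8.2.1, make the main analysis of the count a log-link model (Poisson with robust SE, or negative binomial). Use as offset the log of time from first dose to last recurrence assessment, capped at Week 24 or Week 36. Include the same factors as the other efficacy models: treatment, Country and uncontrolled diabetes. Report the rate ratio and each arm's rate with 95% CIs. State in one sentence that women who leave early contribute their observed episodes and observed time.

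Say whether the model is fitted by recurrence category or only overall. Summarise categories too rare to fit, for example with no events in an arm, descriptively or with exact intervals. Keep the completer repeat as a labelled sensitivity analysis. List the change in Section 11.

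The cost is SAP wording and one procedure call. The time-to-first-recurrence analysis already uses first-dose, recurrence and last-assessment dates, so no new data are needed.

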#### **4.2. Randomization, Stratification and Blinding**

Approximately 320 subjects are planned to be enrolled into the open-label Acute Phase of the study in order to randomize approximately 240 subjects at a 1:1 ratio to one of the two study treatment groups.

An interactive web-based response system (IWRS) will be used to administer the randomization schedule. Biostatistics will generate the randomization schedule using SAS® software Version 9.3 or later (SAS Institute Inc, Cary, North Carolina) for IWRS, which will link sequential subject randomization numbers to treatment codes.

Neither the subjects nor the investigators will be aware of the treatment assignment for the subjects. The study drugs will be identical in number and appearance. Blinding will be maintained throughout the study by use of active or placebo dosage forms of similar appearance.

A subject's treatment assignment will not be broken until the end of the study unless medical treatment of the subject depends on knowing the study treatment the subject received. In the event that the blind needs to be broken because of a medical emergency, the investigator may unblind an individual subject's treatment allocation. As soon as possible, the investigator should first contact the medical monitor to discuss the medical emergency and the reason for revealing the actual treatment received by that subject. No investigator is in full rights to unblind a subject on medical reasons without prior consultation with the sponsor or medical monitor.

Eligible subjects will be stratified at randomization based on the presence or absence of uncontrolled diabetes mellitus, defined as A1C levels  $\geq 8.00\%$  at Baseline (Uncontrolled diabetes mellitus: YES or NO), and by geographical region (USA or Ex-USA).

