#### 8.1.1. Primary Analysis

The primary efficacy analysis will be performed on the ITT set at the TOC visit and will compare the proportion of subjects, in the treatment and placebo groups, who have documented Clinical Success up to Week 24 (TOC).

The number and percentage of subjects with documented clinical success up to the TOC visit will be presented by treatment group. Meanwhile, the number and percentage of subjects with clinical

failure will be presented by the recurrence categories. A Cochran Mantel Haenszel (CMH) test adjusted for Country and uncontrolled diabetes mellitus (Yes or No) at baseline will be performed to assess the statistical significance of a difference between treatment groups in the primary efficacy analysis. Mathematically stated:

$H_0$ : Clinical Success Rate up to Week 24 (TOC) Oral ibrexafungerp 300-mg dose = Clinical Success Rate up to Week 24 (TOC) Placebo

$H_1$ : Clinical Success Rate up to Week 24 (TOC) Oral ibrexafungerp 300-mg dose  $\neq$  Clinical Success Rate up to Week 24 (TOC) Placebo

The p-value, relative risk and 95% confidence interval (CI) will be presented in the ibrexafungerp 300-mg treatment arm compared to the placebo arm. Subjects who have one or more of the required assessments of potential recurrence not completed prior to or at Week 24 (TOC) visit or subjects who withdraw from the study early will be imputed using the imputation rules described in [Section 4.4.1](#).

A sensitivity analysis using the ITT set will be performed where subjects with the imputed clinical outcome will be removed from the analysis.

Subgroup analyses will be performed in the ITT set depending on BMI category ( $\leq 35$  kg/m^2 or  $>35$  kg/m^2), geographic region (USA and EX-USA), Race (White, Black or African American, Asian, American Indian or Alaska Native, Native Hawaiian or Other Pacific Islander, and Other), Uncontrolled diabetes mellitus (Yes or No), Ethnicity (Hispanic or Latino, Not Hispanic or Latino), Number of recurrent VVC episodes in the prior year ( $<4$  times,  $\geq 4$  times) and Candida species at screening (by Genus species), severity of VVC at screening (2 categorizations of the composite score of the vulvovaginal signs and symptoms at screening will be used to evaluate the severity of VVC at screening:  $<7$ ,  $\geq 7$  and '4 - 7', '8 - 12', and ' $\geq 13$ ').

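### SAP 8.2.1 asks a proportional-odds model for a relative risk it does not estimate, and its recurrence-count ANOVA leaves out the diabetes stratum that SAP Section 11 adds to the efficacy models

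*SAP*

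**What the plan says.** SAP 8.2.1 analyses the number of recurrences from Baseline to Week 24 and to Week 36 in two ways.

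- **Count.** For the absolute number of recurrences, "a two-way analysis of variance (ANOVA) model including effects for treatment group and Country will be performed". A rerun restricted to women who completed the visit follows in the same paragraph.
- **Ordered categories** (0, 1, 2 to 3, 4 or more episodes). Here "a proportional odds model will be fitted accounting for the effects of treatment, Country, and uncontrolled diabetes mellitus (Yes or No) at baseline". If proportional odds is violated, alternatives with a weaker assumption will be considered. The reporting sentence is "The p-value, relative risk and 95% CI will be presented in the ibrexafungerp 300-mg treatment group compared to the placebo arm".

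SAP 8.1.1 has almost the same reporting sentence for the CMH test of the binary primary endpoint: "The p-value, relative risk and 95% confidence interval (CI) will be presented in the ibrexafungerp 300-mg treatment arm compared to the placebo arm".

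SAP Section 11 lists the departures from the protocol. One bullet moves the continuous efficacy endpoints from a two-way ANOVA to MMRM and ANCOVA, and excepts the absolute number of recurrences. A separate bullet reads "Add the randomization stratification factor, uncontrolled diabetes mellitus (Yes or No), as justification factor in the efficacy analyses models" and excepts no endpoint. A third replaces site by Country. On the stratum itself, SAP 4.2 says "Eligible subjects will be stratified at randomization based on the presence or absence of uncontrolled diabetes mellitus"; region is the other stratification factor.

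Protocol 18.6.2 specifies the proportional-odds model with treatment and site and names no effect measure for it.

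**The concern.** A proportional-odds model yields one number for treatment: the odds ratio for being at or below a category, assumed the same at every cut. A relative risk is a different quantity. With four categories there are three possible relative risks, and they differ even when the odds ratio is constant. The sentence suits the CMH analysis in SAP 8.1.1, where the outcome is binary and a relative risk exists. In SAP 8.2.1 it leaves the programmer either to print the odds ratio under the wrong name or to choose a cut-point that the plan has not fixed.

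The second problem is one of consistency. Two adjacent paragraphs model the same episodes with different adjustment sets, and the count ANOVA takes up only one of the two covariate changes in SAP Section 11: it has Country in place of site but no diabetes term.

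**Working it through.** **Inputs.** Planning rates of 65% and 43%, 90% power, alpha 0.05 and about 240 subjects at 1:1 (SAP 4.1; Protocol 18.1); two-sided tests (SAP 4). The documents give no distribution of recurrence counts, no prevalence of uncontrolled diabetes and no dropout rate, so anything resting on these is an assumption.

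**The plan's own figure.** Exact two-sided Fisher power by full enumeration at 120 per arm, 65% v 43%, is 0.909. The stated 240 reproduces, and nothing below depends on it being wrong.

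**Step 1: category shares (Poisson, no dropout assumed).** The mean is minus the log of the share with no episode: −ln(0.65) = 0.431 and −ln(0.43) = 0.844.

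| Episodes | Ibrexafungerp | Placebo |
|---|---|---|
| 0 | 0.650 | 0.430 |
| 1 | 0.280 | 0.363 |
| 2 to 3 | 0.069 | 0.196 |
| 4 or more | 0.001 | 0.011 |

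**Step 2: odds ratio and relative risk at each cut.** With cumulative shares a (active) and b (placebo), OR = [a/(1−a)]/[b/(1−b)] and RR = a/b. Ratios use unrounded shares.

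| Cut | a | b | OR | RR |
|---|---|---|---|---|
| 0 | 0.650 | 0.430 | 2.46 | 1.51 |
| 0 to 1 | 0.930 | 0.793 | 3.47 | 1.17 |
| 0 to 3 | 0.999 | 0.989 | 10.77 | 1.01 |

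The maximum-likelihood common odds ratio from a proportional-odds fit to these shares is 2.62.

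**Step 3: does this depend on Poisson?** With assumed gamma overdispersion and the same shares with no episode, at shape 2, 1 and 0.5 the common odds ratio is 2.69, 2.76 and 2.87. The relative risk stays 1.51 at the first cut and is 1.24, 1.30 and 1.38 at the second and 1.05, 1.10 and 1.22 at the third.

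**Step 4: does it depend on proportional odds failing?** No. Fix the odds ratio at 2.46 at every cut and assume a placebo split of 43/25/22/10%. The relative risks of being at or below each cut are then 1.51, 1.24 and 1.06. Under two other assumed splits (43/35/17/5 and 43/15/25/17) the second is 1.15 to 1.33 and the third 1.03 to 1.11. Stated as recurrence, the first cut gives OR 1/2.46 = 0.41 against RR 0.35/0.57 = 0.61.

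**Step 5: leaving out diabetes.** With allocation balanced within strata, omitting a factor of prevalence q that shifts the mean by d, with residual SD s, inflates the treatment standard error by √(1 + q(1−q)d²/s²). At q = 0.05, d = 1 episode and s = 1.2 this is √(1 + 0.0475/1.44) = 1.016. Over q = 1% to 10% and d = 0.5 to 1.5 it runs from about 0.1% to 7%. Simulated counts (240 subjects, 43% with no episode overall, 20,000 replicates, assumed prevalence 2.5% to 10% and rate ratio 1.5 to 3) give a standard error overstated by 0.3% to 11%. Type I error is 2.8% to 5.0% without the factor and 4.8% to 5.2% with it. At 5% prevalence and rate ratio 2, the overstatement is 2.0% and the type I error without the factor is 4.5%.

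**The case against.** **On the effect measure.** This is a label on an other secondary endpoint. The model, its covariates and its p-value stand, and nothing in the documents says an odds ratio will actually be printed as a relative risk. Relative risks of remaining recurrence-free are already planned through the CMH analyses in SAP 8.1.1 and 8.2.1. The Poisson example is not itself proportional, and the SAP has a fallback for that case. All of this is fair, and it limits the consequence. It does not supply the missing cut-point or conversion, and Step 4 shows the mismatch remains when proportionality holds exactly.

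**On diabetes.** Section 11 leaves the count endpoint out of the move away from a two-way ANOVA, and two-way means two factors, so SAP 8.2.1 can be read as following that bullet. This stands far enough that the passages should be called inconsistent, not one of them plainly wrong. The exception covers only the switch to MMRM and ANCOVA; the diabetes bullet has none. The upper end of the range in Step 5 also has no documentary support, since Protocol 11.1 requires good general health.

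**A stronger reading.** The completer rerun, "Additionally, same analysis will be performed to only include those subjects who completed the specified visit based on the ITT set", sits in the ANOVA paragraph and none is stated for the ordered model. A reader might infer that a recurrence-free woman who leaves early is counted as having 0 episodes. The documents do not establish that. SAP 4.4.1 applies its failure rule to the responses in Section 8.2.1, and Protocol 18.4 assigns subjects without a Week 24 assessment as treatment failures. What can be shown is narrower: neither says which of the four categories a failure falls in. No document requires a completer rerun for this endpoint.

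**Conclusion.** Two points hold.

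1. The relative-risk request is wrong as written for a proportional-odds model. At the planning rates the model's parameter is about 2.6 under Poisson counts (2.7 to 2.9 under the assumed overdispersion), against a largest cut-specific relative risk of 1.51. Printed under the planned label it would overstate the effect. The mismatch itself needs no assumption; its size rests on the assumed count distribution and on no dropout.
2. The count ANOVA and SAP Section 11 are inconsistent over uncontrolled diabetes and must be reconciled. The omission is conservative and probably small, though the documents give no prevalence from which to size it.

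The unmapped failure rule is a lesser gap in specification, not a shown error. The primary and key secondary analyses and the sample size are unaffected.

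**What to change.** In SAP 8.2.1:

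- (a) For the ordered endpoint, replace the relative risk by the common odds ratio with its 95% CI, and state its direction. If proportional odds is rejected, report the effect measure of the alternative model under its own name.
- (b) Add uncontrolled diabetes (Yes or No) at baseline as a factor in the count ANOVA and drop the label two-way, so that the paragraph agrees with Section 11.
- (c) As a lesser clarification, say how recurrence-free women who do not complete the visit enter the four categories, consistently with SAP 4.4.1 and Protocol 18.4.

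An analysis of observed episodes, a completer rerun of the ordered model, or a rate-ratio model that allows for overdispersion may be added as sensitivity analyses; these are optional. The cost is a few wording changes and one model term in standard SAS procedures, with no new data.
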